5.2 Dose Determination for Buprenorphine and Tramadol

Based on our clinical experience and earlier studies barring exceptions, the typical MEDD dose of standard-of-care regimens, such as oxycodone, morphine and fentanyl patch used in the treatment of radiation-induced mucositis can range from 20 to 90 mg. Buprenorphine is a potent opioid substitute but there is no consensus at equipotency ratio for morphine to transdermal buprenorphine. Some authors have reported that it lies somewhere between 75:1 to 100:1.(34) This makes finding the appropriate morphine equivalent daily dose (MEDD) for buprenorphine in controlling mucositis-related pain a challenging task. For our study, we used 75:1 equipotency ratio to calculate our morphine equivalent daily dose (**Table 1**). As transdermal buprenorphine is a long-acting medication, we plan to allow tramadol 50 mg (total daily dose) as needed for breakthrough pain up to 400 mg/day (total daily dose), which roughly translates to 5 mg to 40 mg MEDD. Steady-state plasma buprenorphine concentration levels are achieved by day 3, during the first application of buprenorphine. Therefore, it can be titrated after a minimum of 72 hours. We hope to evaluate the possibility of using tramadol to facilitate dose adjustment of buprenorphine. With the buprenorphine and tramadol combination, we hope to provide MEDD to patients which is comparable to other standard-of-care opioids. There is no clear consensus definition of adequate and inadequate pain relief in this setting. However, it is well known that a VAS pain score of $\leq 3/10$ is considered mild intensity pain in multiple settings. Based on some earlier studies and the titratability of TD buprenorphine dose, we have defined adequate analgesia as VAS $\leq 3/10$ for 72 hours, inadequate analgesia as VAS $> 3/10$ for 72 hours, and unbearable pain as VAS $> 3/10$ for 96 hours.(16, 17) If patients have unbearable pain (VAS $> 3/10$ x 96 hours) despite being on highest dose of the buprenorphine patch and tramadol, then, we will switch from tramadol to oxycodone for breakthrough pain and continue treatment with buprenorphine. We will titrate this combination as needed for pain control until study completion. Some authors have also shown the benefit and safety of using immediate-release oxycodone in conjunction with transdermal buprenorphine for moderate to severe pain.(35) If the pain is still uncontrolled $> 3/10$ for 72 hours, even after using oxycodone 90 mg/day with buprenorphine 20 μ g/hour, then, the patient will be taken off the study regimen. However, data monitoring will continue. Patients suffering intolerable side effects (severe constipation, vomiting, headache, pruritis, sedation, or respiratory depression, etc.) or those who wish to switch to standard-of-care oxycodone due to ineffective pain control or unclear reasons at any time during the study will be taken off study regimen. However, data monitoring through the pain app and questionnaires will continue. The dose titration schedule is illustrated in **Table 2**.

5.3 Morphine Daily Dose Equivalent of TD Buprenorphine

Table 1:	
Buprenorphine patch	Morphine equivalent daily dose
5 mcg/hr	9 mg
10 mcg/hr	18 mg
15 mcg/hr	27 mg
20 mcg/hr	36 mg

5.4 Drug Regimen Titration Schedule

Table 2 Drug Titration Schedule

Drug: Buprenorphine with tramadol for breakthrough pain (**First seven weeks of study**) $T = 0 - 7$ weeks;

Start TD buprenorphine 5 μ g/hour along with oral tramadol 50 mg to 150 mg (total dose over 24 hours) as needed for breakthrough pain when mucositis related pain is $\geq 4/10$ on VAS measured on OM Pain App and BPI. Further dose adjustments will be made through pain app.

- If VAS is $>3/10$ for 72 hours on tramadol 150 mg (total dose over 24 hours) and buprenorphine 5 μ g/hour, then, increase tramadol to 250 mg (total dose over 24 hours).
- If VAS is $>3/10$ for 72 hours, even with tramadol 250 mg (total dose over 24 hours) and buprenorphine 5 μ g/hour, then, increase dose of buprenorphine to 10 μ g/hour.
- If the pain persists VAS $>3/10$ for 72 hours on tramadol 250 mg (total dose over 24 hours) and 10 μ g/hour, then, increase the dose of tramadol to 350 mg (total dose over 24 hours).
- If VAS pain is $>3/10 \times 72$ hours with both tramadol 350 mg (total dose over 24 hours) and buprenorphine 10 μ g/hour, then, increase dose of buprenorphine to 15 μ g/hour.
- If VAS pain $>3/10 \times 72$ hours on tramadol 350 mg (total dose over 24 hours) and 15 μ g/hour of buprenorphine, then, increase the dose of tramadol to 400 mg (total dose over 24 hours) and buprenorphine to 20 μ g/hour.
- If the pain persists and is unbearable at $>3/10$ for 96 hours, despite being on highest dose of both drugs, then, replace tramadol with oxycodone at the clinician's discretion up to 90 mg (total dose over 24-hour period) for pain relief.
- If VAS is $\leq 3/10$ maintained for 72 hours, then, we can start tapering off total daily tramadol dose by 50 mg every day, but not change the buprenorphine dose during the first seven weeks of treatment, as mucosal injury from ongoing radiation may increase pain later.

(Post-radiation period) $T = 8 - 12$ weeks: if necessary, increase dose of buprenorphine up to 20 mcg along with tramadol up to 400 mg/day as per titration schedule used in the first seven weeks until VAS is $\leq 3/10$. If pain is well controlled (VAS $\leq 3/10 \times 72$ hours), start weekly tapering of buprenorphine by 5 mcg and tramadol by 50 mg daily.

Special Circumstances

If pain is uncontrolled with VAS $>3/10 \times 72$ hours on 90 mg oxycodone (total dose over 24-hour period) and 20 μ g/hour of buprenorphine, then, buprenorphine patch can be taken off and other stronger pain medications can be started at clinician's discretion. If the patient is admitted and requires IV pain medication for pain control, then, the study drug regimen will be held, and data monitoring will stop for that time. The patient can be discharged on the study regimen (tramadol and buprenorphine) or a combination of oxycodone and buprenorphine patch or any other combination at clinician's discretion, and data monitoring will resume.

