1.3 Rationale for Using Buprenorphine and Tramadol to Manage Radiation-Induced Mucositis Pain

Buprenorphine is a potent pain medication with a more favorable side effect profile and lower habit-forming potential compared to other opioids.(9, 10) It is a derivative of the thebaine, which has mixed opioid agonistic activities (agonistic effect on μ opioid and the OR L1 receptors but the antagonistic effect on kappa and delta opioid receptors).(11) Transdermal buprenorphine, with its active polymeric matrix, is superior to some of the other long-acting opioids in terms of therapeutic efficacy and compliance. Unlike other opioids, it has a ceiling effect, which means its effects increase until the person takes a certain amount; then, these effects level off, which limits euphoria, confusion, and respiratory depression.(12) Earlier studies have shown that buprenorphine suppresses opioid withdrawal and craving, and reduces illicit opioid use.(13) Furthermore, it can safely be administered with no dose adjustments in patients suffering from chronic kidney disease or those who develop chemotherapy-related acute renal failure. This unique characteristic of buprenorphine makes it a good option for mucositis-related pain control in HNSCC patients being treated with commonly used cisplatin-based chemotherapy, which is often associated with acute kidney injury.(14) With appropriate education, patients may perceive buprenorphine to be less addictive than other opioids and its use may be more acceptable. As a result, this may contribute to better pain control and compliance during treatment. Tramadol is a short-acting, weak opioid, which works by both monoaminergic and opioid mechanisms and has

synergistic activity with other long-acting opioids.(15) It is associated with lower incidence of cardiorespiratory depression and reduced dependence compared to strong opioids.

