7.2.8 Dose Adjustment in Liver Failure

No dose adjustment is required in mild to moderate liver failure (Child Pugh class A and B).

Restrict dose to 50 mg q12 in severe liver impairment. **Refer to Table 4**

Table 4. Dose Modifications of Buprenorphine and Tramadol

Table 4:	Buprenorphine Patch	Oral Tramadol
Organ Impairment		
Renal: Creatinine clearance >30ml/min.	No dose adjustment.	No dose adjustment.
Renal: Creatinine clearance <30ml/min.	No dose adjustment.	Restrict maximum daily dose of tramadol immediate release to 200 mg/day.
Mild to moderate liver failure (Child Pugh class A and B).	No dose adjustment.	No dose adjustment.
Severe liver failure (Child Pugh C).	Not studied in severe impairment.	Restrict dose to 50 mg q12 in severe liver impairment.
Cytopenia's (any grade).	No dose adjustment required.	No dose adjustment required.
Other side effects, such as severe nausea, vomiting, headache, respiratory depression, somnolence, dizziness, and constipation.	Dose adjustment at clinician's discretion.	Dose adjustment at clinician's discretion.
Prolonged QTc>500 msec attributable to buprenorphine (other causes ruled out).	Hold buprenorphine patch until QTc comes back to normal range <470 msec	Not applicable

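### Table 2 has no written buprenorphine or oxycodone escalation step, within the study regimen, for a patient under a Table 4 tramadol cap

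*Combined protocol and SAP*

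**What the plan says.** **The ladder (section 5.4, Table 2).** Treatment starts with buprenorphine 5 mcg/h and "oral tramadol 50 mg to 150 mg (total dose over 24 hours) as needed for breakthrough pain". If VAS stays above 3/10 for 72 hours on tramadol 150 mg, the instruction is "then, increase tramadol to 250 mg (total dose over 24 hours"). Buprenorphine then rises only in these circumstances, each after 72 hours of VAS above 3/10:

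- 5 to 10 mcg/h: pain persists "even with tramadol 250 mg (total dose over 24 hours) and buprenorphine 5" mcg/h.
- 10 to 15 mcg/h: pain persists "with both tramadol 350 mg (total dose over 24 hours) and buprenorphine 10" mcg/h.
- 15 to 20 mcg/h: pain persists on tramadol 350 mg and buprenorphine 15 mcg/h. The same step takes tramadol to 400 mg.

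Oxycodone enters when pain has lasted 96 hours "despite being on highest dose of both drugs, then, replace tramadol with oxycodone". Weeks 8 to 12 reuse the same schedule.

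**The caps (sections 7.2.7, 7.2.8 and Table 4).** For creatinine clearance below 30 ml/min: "Restrict maximum daily dose of tramadol immediate release to 200 mg/day". For severe liver impairment: "Restrict dose to 50 mg q12 in severe liver impairment", which is 100 mg/day. For buprenorphine, Table 4 asks for no renal adjustment.

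**Why on-study impairment is in view.** Section 1.3 gives the absence of renal dose adjustment as a reason for choosing buprenorphine in patients receiving "cisplatin-based chemotherapy, which is often associated with acute kidney injury". Inclusion criterion 8 in section 4.10 checks organ function at entry, and states its clearance limit only for patients whose creatinine is above normal.

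**The concern.** Two dosing instructions in the same protocol cannot both be followed for one group of patients. Take a patient whose clearance falls below 30 during chemoradiation and whose pain is uncontrolled. Following Table 2 to its next buprenorphine step means giving tramadol above the Table 4 cap. Respecting Table 4 means the trigger for that step is never met. Neither table refers to the other, and no step is written for a capped patient.

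The result runs against the stated rationale. The drug chosen partly because it needs no renal adjustment cannot be raised, because the drug paired with it is capped. At stake is the management of patients in uncontrolled pain. There is also a question of interpretation: a patient held back by conflicting tables could not be told apart in the data from one in whom the full regimen was tried and failed.

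**Working it through.** **Step 1: compare each trigger with each cap.** Doses are total tramadol per 24 hours. Triggers are from Table 2 and caps from Table 4 (50 mg × 2 = 100 mg for the hepatic cap).

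| Table 2 step | Tramadol needed to trigger it | Tramadol after it | Renal cap 200 mg | Hepatic cap 100 mg |
|---|---|---|---|---|
| Tramadol to 250 (buprenorphine 5) | 150 | 250 | Trigger reachable, target exceeds cap | Trigger out of reach |
| Buprenorphine 5 to 10 | 250 | 250 | Out of reach | Out of reach |
| Tramadol to 350 (buprenorphine 10) | 250 | 350 | Out of reach | Out of reach |
| Buprenorphine 10 to 15 | 350 | 350 | Out of reach | Out of reach |
| Buprenorphine 15 to 20, tramadol to 400 | 350 | 400 | Out of reach | Out of reach |
| Switch to oxycodone | 400 (with buprenorphine 20) | replaced | Out of reach | Out of reach |

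All three buprenorphine increases and the oxycodone switch need tramadol above both caps. The dose needed for the switch is 400/200 = 2 times the renal cap and 400/100 = 4 times the hepatic cap.

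**Step 2: reproduce the protocol's conversions.** Section 5.2 uses 75:1, so the daily morphine equivalent of a patch is mcg/h × 24 / 1000 × 75.

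- 5 mcg/h: 5 × 24 / 1000 × 75 = 9 mg
- 10, 15 and 20 mcg/h: 18, 27 and 36 mg

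These match Table 1 exactly. Section 5.2 converts tramadol 50 to 400 mg as 5 to 40 mg, a factor of one tenth.

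**Step 3: where a capped patient stops if no buprenorphine increase has yet occurred.**

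- Top of Table 2: 36 + 40 = 76 mg.
- Renal cap, Table 2 read literally: the 250 mg step is barred, so tramadol stays at 150 mg and the total is 9 + 15 = 24 mg (24/76 = 32%).
- Renal cap, tramadol allowed up to the cap although 200 mg is not a Table 2 step: 9 + 20 = 29 mg (29/76 = 38%).
- Hepatic cap: 9 + 10 = 19 mg (19/76 = 25%).

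A patient capped later keeps the buprenorphine step already reached. For example, at 10 mcg/h with tramadol at the renal cap the total is 18 + 20 = 38 mg.

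**Step 4: look for other written routes to analgesia.**

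- Section 5.2: a patient with ineffective pain control may move to standard-of-care oxycodone at any time. The patient then leaves the study regimen and data collection continues. Section 8.7 relies on this provision in justifying the absence of a stopping rule.
- Section 5.4, Special Circumstances: after admission for IV analgesia, a patient may be discharged on oxycodone with the patch, or on another combination chosen by the clinician.
- Section 5.2 again: patients already switched to oxycodone take no tramadol, and that combination is titrated as needed.

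The first leaves the regimen, the second requires an admission, and the third applies only after the switch. None is a next step within the regimen for an outpatient who is capped partway up the ladder.

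**The case against.** Several points on the other side stand.

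- A reader might infer that a capped patient can never receive stronger analgesia. The documents do not support that: the routes in sections 5.2 and 5.4 exist, and buprenorphine steps already reached are not reversed. What is missing is the next step inside the regimen.
- A reader might infer that a patient whose tramadol is reduced for side effects is equally blocked. The side-effect row of Table 4 sets no cap and leaves adjustment of both drugs to the clinician, so the conflict is confined to the renal and hepatic rows.
- A reader might infer that these patients become non-responders and lower the chance of reaching 10 of 18. No rule says so. The endpoint is the week 9 BPI worst-pain score in treated patients (2.4, 8.3), data continue to be collected off regimen (4.11, 5.2), and neither stopping the regimen nor taking oxycodone is defined as failure. A capped patient relieved by oxycodone could score as a responder, and one treated for under two weeks might not be evaluable (8.6).
- Few patients are likely to be affected. Inclusion 8 requires bilirubin below 2 mg/dL and, where creatinine is raised, clearance above 30. Section 1.3 speaks of acute kidney injury, not specifically of clearance below 30, and nothing suggests that severe liver failure will arise within 12 weeks.
- The renally capped totals of 24 and 29 mg lie inside the 20 to 90 mg that section 5.2 calls typical for standard-of-care regimens. The 19 mg total lies just below it.

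One rescue does not work. The top dose in the oxycodone rule could be read as the patient's own capped maximum, but the text does not say so, and the buprenorphine steps name tramadol doses outright. The objections narrow the point without removing the collision between the two tables.

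**Conclusion.** Tables 2 and 4 conflict. A patient under a Table 4 tramadol cap has no written buprenorphine or oxycodone escalation step within the study regimen beyond the one already reached. This follows from the text and needs no assumption about frequency.

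The sizes in Step 3 rest on the protocol's own conversion factors and apply only to a patient capped before any buprenorphine increase. The renal range of 24 to 29 mg reflects the two readings of where tramadol stops. The 19 mg hepatic case is a bound and is unlikely to arise.

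The documents give no rate of on-study capping, so no effect on the primary test can be calculated. The stated design is unaffected: a rule of 10 or more responders in 18 gives a one-sided type I error of 0.0405 at 33% and power of 0.816 at 63%, as planned. The case for correcting the text is that two explicit dosing instructions collide for patients in uncontrolled pain, in a situation that section 1.3 foresees for renal failure.

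**What to change.** Reconcile Table 2 with sections 7.2.7, 7.2.8 and Table 4, and cross-refer them, so that the protocol states what happens to a patient under a tramadol cap whose pain is uncontrolled. Whether such a patient moves to another step, leaves the regimen or is handled in some other way is for the sponsor's clinicians to decide. This review proposes no dose or rule. State also whether the top-dose condition for the oxycodone switch refers to the Table 2 maximum or to the patient's permitted maximum.

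Add a CRF field recording whether and when titration was limited by a Table 4 cap, so that these patients can be identified when response and regimen discontinuation are reported.

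The cost is amendment text and one CRF field, with no extra patients, visits or procedures.

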4. Record of opioid pain medications, laxatives, and antiemetic use from the patient's drug diary will be copied by investigators on weekly clinic visits. This will commence after starting treatment. a) Patients will document pain and supportive medication use data daily in their diaries but that information will be verified and recorded by investigator/research coordinator during weekly clinic visits in the electronic medical record(EMR). This data is currently being collected in a section of pain app. Patients average weekly VAS pain scores (question 3 of BPI questionnaire) will also be documented in EMR during weekly clinic visits as per standard of care and can be used for study purposes.
5. The Oral Mucositis (OM) Pain App will be evaluated by the study team on a daily basis through a real-time pain assessment tool in the mobile app. Patients can start using the OM Pain App before starting therapy to familiarize themselves with the instrument. b) Pain app readings will be recorded up to four times/day. The daily pain data will be analyzed by the UWM research team on a weekly basis.
6. All questionnaires/forms can be recorded on weekly in-person visits from weeks 1–7 then completed weekly through in-person/telephone interviews by CTO staff from week 8–12. Other assessments can also be done over phone during week 8, 10 and 11. Window period of +/-3 days will be allowed for data collection.
7. EKG will be done at screening and then on week 7 and 12 if the patient is on treatment with Buprenorphine patch.
8. Digital photos will be taken to document mucositis on the day of enrollment, treatment initiation, then during week 9 and week 12 clinic visits.

=

LIST OF ABBREVIATIONS

AE	adverse event
ALP	alkaline phosphatase
ALT	alanine aminotransferase
ANC	absolute neutrophil count
AST	aspartate aminotransferase
AUC	area under the curve
BPI	Brief Pain Inventory
BUN	blood urea nitrogen
CBC	complete blood cell (count)
CDK	cyclin-dependent kinases
CQ	chloroquine
CR	complete response
CRC	clinical research coordinator
CRF	case report form
CSF	cerebral spinal fluid
CT	computerized tomography
CTCAE	Common Terminology Criteria for Adverse Events
CTL	cytotoxic T cell
CTO	Clinical Trials Office
DFS	disease-free survival
DLT	dose-limiting toxicity
DSMC	Data and Safety Monitoring Committee
DSMP	data and safety monitoring plan
ER	estrogen receptor
FDA	Food and Drug Administration
GCP	good clinical practice
GVHD	graft-versus-host disease

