2.4 Primary Endpoint

Establish the efficacy of the study regimen by showing that at least 33% of the patients will achieve at least a 30 percent decrease in the VAS pain score on the BPI questionnaire (question 3: worst pain in last 24 hours) from baseline to the end of week 9 of treatment and the follow-up period. Earlier studies have shown that the VAS pain score($\geq 4/10$) on the day of

treatment initiation may be used as the baseline in this setting and a 30% or higher reduction in the baseline pain score is a sign of a meaningful drug response.(27-29)

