8.8 Missing Data

Missing data will be investigated, and multiple imputations will be used to account for missingness. Multiple imputations will be performed under the assumption that missing data are missing at random (MAR). If the validity of the MAR assumption is questioned, possible departures from MAR will be investigated by sensitivity analyses.

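### Pain data stop during admission for IV analgesia; if the admission covers week 9, the primary outcome is missing because of pain yet imputed as missing at random

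*Combined protocol and SAP*

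**What the plan says.** - **Pause during admission.** Section 5.4 (Special Circumstances): when a patient is admitted and requires IV pain medication, "the study drug regimen will be held, and data monitoring will stop for that time". The pause ends at discharge. The patient may leave on the study regimen, on oxycodone with the patch, or on "any other combination at clinician's discretion, and data monitoring will resume".
- **No pause for other departures.** Section 5.2, on patients who leave the regimen for side effects, ineffective pain control or by choice: "However, data monitoring through the pain app and questionnaires will continue". Section 4.11 keeps study procedures going after treatment stops. Section 8.7 says that pain monitoring continues even after discontinuation for lack of efficacy.
- **Primary endpoint.** Section 2.4 uses one change in BPI question 3, "from baseline to the end of week 9 of treatment and the follow-up period". Study Calendar footnote 6 sets the timing: "Window period of +/-3 days will be allowed for data collection". The same footnote lets staff complete questionnaires by telephone in weeks 8 to 12.
- **Missing data.** Section 8.8 prescribes multiple imputation under MAR. If the validity of that assumption is questioned, "possible departures from MAR will be investigated by sensitivity analyses". It names no imputation model, no sensitivity method and no rule for admitted patients.

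**The concern.** The event that stops data collection is pain severe enough to need inpatient IV analgesia, and pain is the outcome being measured. A week-9 score lost this way is not a neutral gap. The protocol follows patients who fail without admission, but stops collecting from those admitted for IV analgesia while they are in hospital. Its only stated handling then treats the gap as MAR.

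The decision rule is ten or more responders out of 18 (Section 8.4), so a single patient can decide the result. If a true failure is imputed as a likely responder, the response rate moves up and the one-sided 5% error is no longer assured.

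**Working it through.** **Inputs.** From Sections 8.4 and 8.6: null rate 0.33, alternative 0.63, n = 18, success at 10 or more, one-sided 5% binomial test, 20 enrolled to allow for 10% dropout. The number of patients in hospital for IV analgesia at week 9 is not given. I assume k = 0 to 4 of 18 and show the range.

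**Step 1: reproduce the stated design (exact binomial).**
- P(X ≥ 10 | 18, 0.33) = 0.0405, below 0.05.
- P(X ≥ 10 | 18, 0.63) = 0.8165, above 80%.
- P(X ≥ 9 | 18, 0.33) = 0.1019, so 10 is the smallest valid cut-off.
- 18 / 0.90 = 20.

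The plan's figures hold.

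**Step 2: effect of the gap.** Suppose that k of the 18 week-9 scores are missing through admission and that all k are true failures. Hold the true overall response rate at 0.33. The rate among observed patients is then q = 18 × 0.33 / (18 − k) = 5.94 / (18 − k). Compare two ways of handling the k patients:
- drawn at the observed rate: P(Bin(18, q) ≥ 10);
- counted as non-responders: P(Bin(18 − k, q) ≥ 10).

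| k | q | Drawn at observed rate | Counted as non-response |
|---|---|---|---|
| 0 | 0.330 | 0.0405 | 0.0405 |
| 1 | 5.94/17 = 0.349 | 0.0591 | 0.0379 |
| 2 | 5.94/16 = 0.371 | 0.0865 | 0.0349 |
| 3 | 5.94/15 = 0.396 | 0.1271 | 0.0315 |
| 4 | 5.94/14 = 0.424 | 0.1867 | 0.0275 |

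**Step 3: dependence on how imputations are combined.** The plan does not say how a binomial test is applied to multiply imputed data. If the average imputed count, 18x / (18 − k) for x observed responders, were compared with 10:
- k = 1: 10 of 17 observed responders are still needed (18 × 9/17 = 9.5 falls short), and the false-success probability is 0.0379, so there is no inflation.
- k = 2: 9 of 16 suffices (18 × 9/16 = 10.1), and the probability is 0.0944.

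For one such patient, crossing 5% therefore depends on the unspecified method. For two, both crude versions exceed it.

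**Step 4: what these figures leave out.** Both versions ignore the patient's own pain history. A model using earlier BPI and app scores would tend to predict non-response for a patient with recorded severe pain, and the bias would be smaller. That is why these are upper-end illustrations.

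**The case against.** **The pause is temporary.** This stands. Monitoring resumes at discharge, so the primary outcome is lost only if the admission covers the week-9 window. Section 2.6 puts the start of the pain peak at weeks 4 to 5, and Section 5.1 puts the greatest toxicity in the first seven weeks, so many admissions may fall earlier. Those leave gaps in app scores, weekly averages and AUC summaries, not in the primary endpoint. Section 5.1 also expects moderate to severe pain in most patients to week 12, so a week-9 admission is not far-fetched.

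**The pause may not cover the BPI.** The text is ambiguous. Section 5.1 lists app monitoring and the BPI as separate items, while Section 5.2 uses the term for both app and questionnaires. Section 4.9 also places the week-9 primary-endpoint data under the app item. Either way the wording needs settling.

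**Stronger readings that the documents do not support.**
- A reader might infer that treatment failures in general become missing. They do not: patients who fail without admission remain under observation.
- A reader might infer that gaps are filled only from patients who stayed on the regimen. Section 8.8 does not say so, and patients who left it would be among those observed.
- A reader might build an example in which 10 of 18 observed responders become an expected 10/18 × 20 = 11.1 of 20, reaching a cut-off of 11 (P = 0.0350), whereas 10 of 20 fails (P = 0.0866). The tail probabilities are right. But the plan's rule is 10 of 18, which those observed patients already meet, and two week-9 admissions are an assumption.

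**A non-responder rule could override real data.** This also stands. Once BPI question 3 is collected in hospital, the score is observed, and overriding it is a choice of estimand. The rule therefore belongs to scores that are still missing, and the wider version to a sensitivity analysis.

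**Conclusion.** The concern holds in a limited form. A stated rule creates a gap driven by pain, the default handling assumes MAR, and no rule classifies the affected patients. The primary endpoint is exposed only when an admission for IV analgesia covers week 9. The bias can be upward, but the documents do not fix its size. With crude imputation at the observed rate, one or two such true failures of 18 take the false-success probability from 0.041 to 0.059 or 0.087. Those figures assume that every such patient is a true failure, that the overall rate is 33%, and that the imputation ignores the patient's earlier scores. The conditional sensitivity analysis in Section 8.8 softens the problem but does not settle it, because neither its trigger nor its method is stated. This does not undermine the design, but it should be corrected because the remedy is cheap and the decision can turn on one patient.

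**What to change.** 1. **Section 5.4, Special Circumstances.** State that the weekly BPI question 3 continues during an admission for IV analgesia, in person or by telephone as footnote 6 already allows in weeks 8 to 12. This changes data collection only, not care.
2. **Section 8.8, primary endpoint.** State that a week-9 score still missing because of such an admission is counted as non-response and is not imputed under MAR.
3. **Section 8.8, sensitivity analysis.** Report, unconditionally, an analysis that counts every patient in hospital for IV analgesia at week 9 as a non-responder, whether or not a score was obtained. A score given under IV analgesia may be low without reflecting the study regimen.

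Cost: amended wording, a few questionnaires by existing staff, and a possibly slightly lower observed response rate. The change does not settle how to classify a patient discharged on other opioids before week 9 whose score has fallen by 30%; that is a separate question about the endpoint.
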